The Corrie DHI program consists of a patient-facing smartphone app which provides education; recommendations for lifestyle modifications; medication, vitals, and exercise monitoring; appointment scheduling and tracking; care team directory; electronic wallet for health and stent cards; the ability to send PDF summary reports to clinicians; and follow-up reminders to optimize cardiac recovery and secondary prevention. The original version of the Corrie Health digital platform was tested in acute MI patients at 4 clinical sites including Johns Hopkins Hospital, Johns Hopkins Bayview, Reading Hospital and Massachusetts General Hospital (MiCORE IRB00099938).¹³ Patient-monitored data flows into secure servers on the backend, providing a source of rich, granular data over time for heart rate, steps, weight, blood pressure, and medication adherence. Corrie is built on Apple and Android platforms.

For the present trial, the original Corrie Health digital platform was adapted to include extensive exercise tracking with pre-and post- exercise data capture along with weekly

Date: 10.09.2024

Principal Investigator: [name], MHS

Application Number: IRB00308410

evaluations and goal setting by a trained “Corrie Coach” to promote behavior change and mental health support. Exercise can be performed anywhere a patient feels comfortable with, including neighborhood gyms or outdoors. Furthermore, patients will be provided with motivational messaging and feedback on progress with their goals. The Corrie Message Bank (attached as supplemental document) has been developed by combining validated messages from the mActive trial,³³⁻³⁵ American Heart Association’s Care Pathway messages, and patient generated messages. The Corrie Clinical Dashboard allows for intuitive data visualization by the clinician of key cardiovascular health metrics including blood pressure, heart rate, steps, medication adherence, exercise, and education completion. The clinician then uses this data to generate actionable insights and provide comprehensive feedback to the patient. The trial intervention has been optimized with input from demographically diverse patients, caregivers and clinicians (IRB00266731). A preliminary version of the intervention is being evaluated in our IRB approved quality improvement project (IRB00248849). Preliminary data from the quality improvement project supports that it is feasible to evaluate the intervention in a RCT.

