the DHI (Table 2), which could promote digitally-enabled hybrid CR uptake at scale and reduce the gap in lifesaving CR access and utilization.

[name], MD, MHS, PI, has extensive clinical and research experience the CR space. She directs the Johns Hopkins Cardiac Rehabilitation Center.

Table 2. Components of DHI: The Corrie Hybrid Cardiac Rehabilitation Program

Patient Level - Corrie App, Smartwatch, Blood pressure monitor, exercise resistance bands, Corrie "Coach" (attached in supplemental documents) and contextual motivational messages (attached in supplemental documents)
Clinician Level – Reminder for CR referral, Reminder for ordering repeat lipid panel upon discharge (as recommended by professional society guidelines), In person assessment and two monitored and supervised sessions for personalization of home exercise, improving confidence and self-efficacy for home exercise, and assessment of safety of home exercise

Figure 1. Core components of Cardiac Rehabilitation/Secondary Prevention Programs as per American Heart Association and American Association of Cardiovascular and Pulmonary Rehabilitation Statement.³⁶

4. Study Procedures

General Overview:

We will conduct a multi-site, parallel arm randomized clinical trial to evaluate the efficacy of the intervention plus usual care compared to usual care alone (1:1 allocation ratio) in individuals who present to study hospitals with the following diagnosis or interventions: ST elevation myocardial infarction (STEMI), Type 1 non ST elevation myocardial infarction (NSTEMI), Atherosclerotic Cardiovascular Disease (ASCVD) requiring coronary revascularization via percutaneous coronary intervention (PCI) or coronary artery bypass graft surgery (CABG), and valvular heart disease interventions including valvular heart surgery and transcatheter aortic valve replacement (TAVR). We will evaluate the primary outcome and secondary outcomes at 12 weeks post-randomization. Study sites include Johns Hopkins Hospital, Johns Hopkins Bayview Medical Center, Howard County Hospital, and Suburban Hospital.

Enrollment, Randomization and Measurements:

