28. At 12 weeks post-randomization follow up, all study participants will receive a survey via REDCap to report any adverse events, including a heart attack, repeat cardiac procedure, stroke, transient ischemic attack, emergency room visit, or hospital readmission. If a patient is readmitted to a Hopkins affiliated hospital or other site's hospital, their EHR will be searched for confirmation and cause of readmission. If the person is readmitted to an outside hospital, we will email them an Authorization for Release of Health Information form asking for permission to obtain their EHR of readmission. If patients cannot be reached, we will contact their emergency contact to

identify whether the patient is alive and also search the EHR. If death is reported, it will be verified by death certificates or through the EHR.

29. At 12 weeks post-randomization follow up, all participants will attend an in-person study visit at Johns Hopkins Bayview Institute for Clinical and Translational Research (ICTR; Clinical Research Unit) site where all measurements outlined in Table 3 will be conducted, including vital signs, blood work for HbA1c and Lipid panel (non-fasting), body measurements, and 6MWT. If a participant cannot attend the final visit at Johns Hopkins Bayview ICTR site due to medical conditions, exceptions can be made to accommodate the participant at another study site. The 6MWT will be performed by ICTR staff blinded to study arm assignment to avoid bias in measurement (compared to the pre-discharge 6MWT for hospital-enrolled patients, which will be obtained by a trained study team member). Participants will be given an option to complete online surveys while attending the in-person study visit. If at either of these time points (baseline and 12 weeks post-randomization), participants do not respond to the online surveys within 7 days, a member of the study team will attempt to obtain their responses to the surveys via a phone interview. In order to accommodate flexible scheduling, we will aim to allow up to 24 weeks for the final study visit. For the ICTR study visit, parking and transportation fees will be covered by the research study budget for all patients.

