Each participant will be enrolled in the study from the time of enrollment during or shortly following hospitalization or cath lab encounter to 12 weeks post-randomization after discharge. Study visits will occur at baseline (at patient bedside or via follow up call) and 12 weeks post-randomization post-discharge (at Bayview Clinical Research Unit, up to maximum 18 weeks post- (to account for delays related to clearance of procedure-related precautions (e.g. sternal precautions following CABG surgery) or insurance approval for starting in-person CR sessions), whichever occurs earlier). Patients in the intervention arm will also be encouraged to have a lipid panel rechecked (ordered by the primary team at discharge) at their local laboratory 4 weeks post-discharge. Patients in the control group will receive reminders from the study team to participate in the final study visit.

Date: 10.09.2024

Principal Investigator: [name], MHS

Application Number: IRB00308410

Blinding

Although blinding participants or study team members enrolling patients is not possible, outcome assessors will be blinded to intervention allocation. We will instruct study participants not to discuss allocation with study personnel prior to both the initial and follow-up assessments.

Definition of treatment failure or participant removal criteria

For participants in the intervention group: If the participant stops using the Corrie DHI for >30 days or does not respond to phone calls after failing to complete the study surveys after 7 days, the participant will be considered lost to follow up.

For participants in the Control group: If the participant does not respond to phone calls after failing to complete the study surveys after 7 days, the participant will be considered lost to follow up.

Description of what happens to participants receiving therapy when study ends or if a participant's participation in the study ends prematurely

When the study ends or a participant's participation in the study ends prematurely, participants in the intervention group may keep their app (in which case their use will continue to be tracked). Any other devices that were provided during the study will be expected to be returned.

Participants may be given the option to participate in future research studies.

5. Inclusion/Exclusion Criteria

Inclusion Criteria

- Adult aged 18 years or older

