For the trial to demonstrate noninferiority with 80% power, assuming a pooled standard deviation of 107 meters for the follow-up 6MWT and a true 6MWT difference in favor of the Corrie HCR program of 30 m, 160 patients will be required (80 per group) to exclude a difference of >12.5 m in favor of the usual care group. The noninferiority margin of 12.5 m was chosen to represent about 40% of the minimum important difference of 30 m in 6MWT as identified in previous studies. Accounting for an attrition rate of 20% during follow-up after randomization, a total of 200 (100 per group) participants will be randomized in a 1:1 ratio to the 2 treatment arms. In order to accrue 200 patients for randomization, we expect to recruit up to 300 patients, until target randomization number has been met. We will compare the mean level of 6MWT at 12 weeks post-randomization between the intervention and control groups using a generalized linear regression model. The sample size calculation was performed using the TWOSAMPLEMEANS statement in SAS version 9.4 procedure PROC POWER (SAS Institute Inc., Cary, NC), in which the null value option was specified to represent the noninferiority margin.

If a participant has an adverse event that results in them being discontinued from the study or does not engage with the intervention, that participant will be included in the intention-to-treat analysis, which is the primary form of analysis for our study.

In addition to the primary intention-to-treat analysis, a pre-specified, per-protocol analysis will be conducted 1) inclusive of intervention group participants who remain active in the study and engage with the intervention, and separately 2) among those participants (in both control and intervention arms) who have completed at least two in-person CR sessions, in order to assess the efficacy of the intervention.

In addition, pre-specified subgroup analyses will be performed, stratified by: age, sex, treatment modality (cardiac surgery, catheter-based intervention, or medical therapy), and LDL-C level (threshold LDL-C \geq 55mg/dL).

8. Risks

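### Stopping the digital intervention for more than 30 days counts as loss to follow-up in the intervention arm only, and the plan does not say that the 12-week walk test is still sought

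*Combined protocol and SAP*

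**What the plan says.** The rule is in section 4 (Study Procedures), under the heading "Definition of treatment failure or participant removal criteria". For the intervention arm it reads "If the participant stops using the Corrie DHI for >30 days or does not respond to phone calls", the calls being those made once surveys are 7 days overdue. Either trigger makes the participant lost to follow-up. The parallel sentence is "For participants in the Control group: If the participant does not respond to phone calls", again after overdue surveys, and it has no second trigger.

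Two other places bear on the same participants:

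- Section 4, item 29, on the 12-week assessment that includes the 6MWT: "all participants will attend an in-person study visit". It makes no exception for people who have stopped using the digital health intervention (DHI).
- Section 7 (Statistical Analysis), on a participant who "does not engage with the intervention, that participant will be included in the intention-to-treat analysis, which is the primary form of analysis".

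The sample size in section 7 allows for loss with one overall rate: "Accounting for an attrition rate of 20% during follow-up after randomization". That rate is not split by arm or by cause of loss.

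**The concern.** Not using the app or devices is a matter of adherence. Being lost to follow-up means that the outcome cannot be obtained. The intervention-arm rule merges the two: a participant who answers the phone and would come to the visit is still classed as lost after more than 30 days without the DHI. Controls cannot be lost in this way.

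If that label decides who is brought in for the walk test, the missing 6MWT values in one arm depend on adherence and the randomized comparison is no longer protected. The primary analysis is a noninferiority comparison with a 12.5 m margin, so a shift of a few metres matters. Section 7 gives no method for missing 6MWT values that could repair the loss afterwards.

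A smaller point is that the amount and kind of use that counts is not defined. Section 3 opens its description with "The Corrie DHI program consists of a patient-facing smartphone app", while Table 2 lists "Patient Level - Corrie App, Smartwatch, Blood pressure monitor, exercise resistance bands" together with the coach. Someone who has dropped the app but still takes coaching calls could be classed either way.

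**Working it through.** **1. The passages side by side.** Take an intervention participant who has not used the DHI for more than 30 days but remains reachable.

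| Place | What follows for this participant |
|---|---|
| Section 4, removal criteria | Lost to follow-up |
| Section 4, item 29 | Attends at 12 weeks and walks |
| Section 7, intention-to-treat | Included in the primary analysis |
| Section 7, first per-protocol set | Left out as not engaged |

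The last three agree with one another and the first does not fit them. Section 7 settles who is analysed, but a participant who is never brought in has no 6MWT to analyse. The retention sentence in item 25 covers only people at high exercise risk. No text gives an order of precedence for collection.

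**2. The plan's own figure.** Section 7 gives SD 107 m, margin 12.5 m, true difference +30 m, 80% power, 80 evaluable per group, and 100 per group after 20% attrition. Alpha is not stated.

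- Standard error = 107 × √(1/80 + 1/80) = 16.92 m.
- Distance from the margin = 30 + 12.5 = 42.5 m; noncentrality = 42.5 / 16.92 = 2.51.
- Power from the noncentral t with 158 df: 80.4% at one-sided 5%, 70.4% at one-sided 2.5%.
- Attrition: 160 / 0.80 = 200.

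The stated size therefore matches one-sided 5%, which is used below as an inference.

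**3. The shift if the loss rule is acted on.** Let p be the share of obtainable intervention-arm outcomes removed, and d the number of metres less that those participants walk than those kept. If K is the mean of those kept, the full-arm mean is (1 − p)K + p(K − d) = K − pd. Removal therefore raises the arm mean by p × d. Neither p nor d is in the documents; the values below are assumptions.

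**4. Effect on the decision.** Two cases are needed. In the first, removals come on top of the planned 20%, leaving 80(1 − p) against 80: 72 when p = 10% and 68 when p = 15%. In the second they fall within the 20%, leaving 80 against 80. At a true difference of −12.5 m the noncentrality is pd / SE; at +30 m it is (42.5 + pd) / SE. SE is 17.38 m for 72 v 80, 17.65 m for 68 v 80 and 16.92 m for 80 v 80. Each cell shows on top / within.

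| p | d (m) | Shift (m) | False noninferiority at −12.5 m | Noninferiority declared at +30 m |
|---|---|---|---|---|
| 10% | 30 | +3.0 | 7.0% / 7.1% | 83.2% / 84.9% |
| 15% | 50 | +7.5 | 11.1% / 11.4% | 88.0% / 90.3% |
| 15% | 0 | 0 | 5.0% / 5.0% | 77.4% / 80.4% |
| 15% | −50 | −7.5 | 1.93% / 1.85% | 62.9% / 66.1% |

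Worked example, second row, on top: 7.5 / 17.65 = 0.425 with 146 df, which gives 11.1%. At one-sided 2.5% the four on-top cases give 3.7%, 6.2%, 2.5% and 0.9% false noninferiority.

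Precision is lost only when removals come on top of the planned attrition. A favourable shift of about 1.2 m (72 v 80) or 1.9 m (68 v 80) offsets that loss; beyond it, the chance of declaring noninferiority rises.

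**The case against.** The strongest reply is that the plan already gives the right answer. Section 7 places in the primary analysis both people discontinued after an adverse event and people who do not engage, so it expects to analyse participants whose study status has ended. Item 29 calls everyone to the visit, and item 28 pursues even unreachable participants through emergency contacts and the health record. The removal paragraph never says that the walk test is withheld. Bias therefore requires staff to infer an instruction from a heading and a label. All of this stands as to analysis, and it is why the harm is conditional. It does not settle collection of the 6MWT: the paragraph is the only operational definition of loss in the document, its heading names removal, and a label of lost is an ordinary reason not to schedule a visit.

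The size is also open to challenge. A deficit of 50 m is 0.47 of the stated SD (50 / 107), and many long-term non-users might not have attended anyway. With p = 5% and d = 20 to 30 m, false noninferiority is only 5.6% to 6.0%. That is fair; the figures illustrate a mechanism and do not predict a bias.

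On scope, section 3 goes on to say that the platform was adapted for this trial to include a coach, and Table 2 is headed as the components of the DHI. The broader reading is therefore the more natural one, and on it fewer people meet the trigger. What remains is that no threshold for use is stated.

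**Conclusion.** The concern holds and should be fixed. The loss definition differs by arm, its extra trigger measures adherence, and it contradicts item 29 and the intention-to-treat statement with no rule of precedence for collecting the primary outcome. That much rests on the text alone and is highly certain.

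Any bias is conditional on staff acting on the loss rule, and its direction cannot be known in advance. Over the illustrated cases (p of 10% to 15%, d from −50 to +50 m, SD 107 m, inferred one-sided 5%), false noninferiority ranges from about 1.9% to 11.4% against a nominal 5%. The sample size itself reproduces and is not at fault.

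**What to change.** Reconcile the removal paragraph with item 29 and section 7:

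1. Delete the 30-day non-use trigger from the loss-to-follow-up definition and use the same contact-based definition in both arms.
2. Record DHI non-use separately as non-adherence, for the per-protocol analysis already planned in section 7, and state which components and how much activity count as use.
3. State that the 12-week 6MWT is sought from, and analysed for, every randomized participant regardless of DHI use.

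The cost is wording only. The visit is already planned for all participants, and the size stays at 80 evaluable and 100 randomized per group.

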To address these critical gaps in the recovery process, participation in CR, and improve secondary prevention for patients with CVD, we developed a multilevel intervention that is based on a digital health strategy using the established Corrie Health platform, with funding from the American Heart Association. Corrie Health is a digital health intervention (DHI) that was originally developed at Johns Hopkins to support acute myocardial infarction recovery.¹³ The Corrie CV multilevel secondary prevention program is designed to deliver Phase I through IV CR. It includes a customized smartphone application (app) with real-time data analytics, supervised exercise, patient education, medication adherence reminders/tracking, LDL cholesterol and hemoglobin A1c level tracking, smartwatch integration (Apple Watch or Fitbit) for physical activity / exercise and heart rate tracking, wireless blood pressure monitor integration, app enabled reminders,

Date: 10.09.2024

Principal Investigator: [name], MHS

Application Number: IRB00308410

health coach guided action plans to promote behavior change and clinician level intervention. Corrie Health delivers an accessible, early intervention from hospital to home, thereby mitigating the conventional barriers to secondary prevention traditionally delivered in-person, e.g., cost, scheduling, and transportation access.¹⁴ While smartphone ownership is increasing in White, Hispanic and Black individuals in the US, smartphone app use is even higher among Black individuals, facilitating access to lifesaving interventions for individuals who have been historically disadvantaged with respect to access to care.^{15, 16}

Overall, we aim to evaluate efficacy and safety of the multi-level Corrie digital health intervention (DHI) in a parallel arm randomized controlled trial (RCT), while ensuring the study protocol promotes evaluation of the DHI secondary prevention program in diverse groups of patients. The DHI will complement usual care, which includes in-person center-based CR, and will be compared to usual care alone. The primary outcome measure of the study is the difference in distance participants walked (i.e. functional capacity) using the 6 minute walk test (6MWT) at final study follow-up (12 weeks post-randomization) between the intervention and usual care groups. The 6MWT is a rigorously validated clinical assessment of functional performance in individuals with cardiovascular disease).^{17, 18}

2. Objectives

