overcome the barriers of access, we will cover transportation and/or parking fees for participants to attend the two required in-person CR sessions using research funds.

Patients will receive prescriptions for exercise from a center-based exercise physiologist during the in-person CR sessions. Even participants who have been randomized to the intervention arm will be encouraged to attend in-person CR sessions, especially at 30-day and 60-days (beyond the first two required in-person CR sessions) to allow for appropriate exercise modifications to their Individualized Treatment Plans by the exercise physiologist. For patients who elect to not continue to attend in person CR sessions beyond the first two sessions, once cleared for home exercise, updated exercise prescriptions will be provided by the study exercise physiologist as per AACVPR guidelines.

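### The aim is efficacy of the DHI added to usual care, but the only sized hypothesis is noninferiority, with no stated alpha and no superiority step

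*Combined protocol and SAP*

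**What the plan says.** The Abstract (Section 1) states the aim: "we aim to evaluate efficacy and safety of the multi-level Corrie digital health intervention (DHI". It describes an add-on comparison: "The DHI will complement usual care, which includes in-person center-based CR, and will be compared to usual care alone". The General Overview in Section 4 repeats it: the trial is to "evaluate the efficacy of the intervention plus usual care compared to usual care alone (1:1 allocation ratio".

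Noninferiority appears only in the sample-size paragraph of Section 7, which opens: "For the trial to demonstrate noninferiority with 80% power, assuming a pooled standard deviation of 107 meters for the follow-up 6MWT". The effect assumed for that calculation is a benefit, given as "a true 6MWT difference in favor of the Corrie HCR program of 30 m". That paragraph requires 80 evaluable patients per group to rule out usual care being better by more than 12.5 m, and raises the total to 200 randomized for 20% attrition. It says PROC POWER was used, "in which the null value option was specified to represent the noninferiority margin".

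The analysis itself is one sentence: "We will compare the mean level of 6MWT at 12 weeks post-randomization between the intervention and control groups using a generalized linear regression model". Intention-to-treat is the primary analysis. No alpha, sidedness, confidence level or superiority hypothesis is given anywhere.

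**The concern.** An add-on comparison asks whether the addition helps. A noninferiority result here would say only that adding the DHI does not cost patients more than 12.5 m of walking distance. The sole sized hypothesis can therefore be met while the stated aim goes unanswered.

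Two things are then left open until the data are in.

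- **The error level.** The margin and direction are clear, but the confidence level at which the margin must be excluded is not. The same result could be called noninferior on a 90% interval and not noninferior on a 95% interval.
- **The claim.** The regression will produce a p-value against zero. If that is later read as a test of benefit, it has no place in a testing order, and the quoted 80% power does not apply to it.

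**Working it through.** **Inputs from Section 7.** SD 107 m; true difference +30 m (intervention minus usual care); margin 12.5 m; 80 evaluable per group; 20% attrition.

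**Assumption.** Alpha is not stated, so both usual levels are shown: one-sided 5% (90% CI) and one-sided 2.5% (95% CI). The comparison is taken as unadjusted because no covariates are named.

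**Step 1: reproduce the planned size.** The distance from the noninferiority null is 30 + 12.5 = 42.5 m. By noncentral t, 80% power needs:
- one-sided 5%: 80 per group (power 80.4%), which matches the plan;
- one-sided 2.5%: 101 per group, which does not match.

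Attrition: 160 / (1 - 0.20) = 200, which matches. The stated size therefore rests on one-sided 5%, which the plan never states.

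**Step 2: power for both questions at 80 per group.** SE = 107 × √(2/80) = 16.92 m, with 158 degrees of freedom. The noncentrality is 42.5/16.92 = 2.51 for noninferiority and 30/16.92 = 1.77 for superiority. Superiority on an interval implies noninferiority on the same interval, so the chance of noninferiority alone is the difference between the two powers.

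| | One-sided 5% (90% CI) | One-sided 2.5% (95% CI) |
|---|---|---|
| Critical t | 1.6546 | 1.9751 |
| CI half-width (t × SE) | 27.99 m | 33.41 m |
| Noninferiority power | 80.4% | 70.4% |
| Superiority power | 54.8% | 42.2% |
| Noninferiority without superiority | 25.6% | 28.3% |
| Noninferiority declared if true difference is 0 | 18.2% | 11.0% |

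**Step 3: observed differences needed.** Noninferiority needs an observed difference above half-width - 12.5; superiority needs one above the half-width.
- 90% CI: 27.99 - 12.5 = +15.5 m, and +28.0 m. At +15.5 m the interval runs from -12.5 to +43.5 m.
- 95% CI: 33.41 - 12.5 = +20.9 m, and +33.4 m.

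Any observed difference between +15.5 and +20.9 m changes verdict with the unstated level. For example, +18 m gives 18 ± 27.99 = -10.0 to +46.0 m (noninferior), but 18 ± 33.41 = -15.4 to +51.4 m (not noninferior).

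**Step 4: no attrition (100 per group).** Noninferiority/superiority power is 87.6%/63.0% at one-sided 5% and 79.8%/50.5% at one-sided 2.5%.

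**Step 5: size for 80% superiority power.**
- One-sided 5%: 158 per group; 316/0.8 = 395 randomized.
- One-sided 2.5%: 201 per group; 402/0.8 = 502.5, so 503 randomized.

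**The case against.** **Noninferiority may be the right first question for hybrid rehabilitation.** Sections 1 and 3 stress barriers to center attendance and wider uptake of hybrid programs, and Section 7 itself uses the hybrid name. Section 4, item 26 makes home exercise prescriptions available "For patients who elect to not continue to attend in person CR sessions beyond the first two sessions", so some substitution for center sessions is possible. This stands as a possible rationale. However, no section connects it to the choice of noninferiority, the same item encourages all patients to keep attending, and the comparison remains add-on. A justified noninferiority test would still not answer the efficacy aim.

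**Efficacy need not mean superiority.** The protocol never states a superiority hypothesis, and the primary outcome is described only as a between-group difference. That is fair on the letter, but with usual care given in both arms, efficacy of the addition has no other natural meaning.

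**The decision rule is mostly there, and the alpha can be recovered.** The margin and null value are given, and 80 per group points to one-sided 5%. The window in which the two levels disagree carries a probability of 80.4% - 70.4% = 10% at a true +30 m and 18.2% - 11.0% = about 7% at a true zero. The ambiguity is bounded, but a level inferred from a sample size is not a pre-specified one.

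**Covariate adjustment could raise superiority power.** To reach 80% with 80 per group, covariates would have to explain about 1 - 80/158 = 49% of the variance (one-sided 5%) or 1 - 80/201 = 60% (one-sided 2.5%). No covariates are named. Table 3 lists the walk test only at 12 weeks, and item 29 mentions a pre-discharge test only for hospital-enrolled patients. A gain of that size cannot be assumed.

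**Keeping the sample size leaves the benefit test underpowered.** True. The proposed change makes the trial's answer to its aim pre-specified and honestly described; it does not make that answer likely.

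**Conclusion.** The concern holds. As written, the trial can meet its only sized hypothesis without evidence of added benefit. If the DHI truly adds 30 m, that happens 26% of the time on a 90% CI and 28% on a 95% CI. Power to show benefit is 55% or 42% at the planned evaluable size, and 63% or 51% with no attrition. The unstated alpha moves noninferiority power from 80% to 70%.

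These figures rest on the plan's own SD, margin and assumed difference, an unadjusted comparison, and the two usual alpha levels. Because this is the success criterion for the primary outcome, it should be settled before the data are analyzed.

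**What to change.** Keep the sample size and revise Section 7:

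1. State the alpha and the single matching interval: 90% CI for one-sided 5%, or 95% CI for one-sided 2.5%.
2. Pre-specify a fixed sequence on that interval in the intention-to-treat analysis, which is already primary. Declare noninferiority if the lower limit of intervention minus usual care is above -12.5 m. Only if that is met, declare superiority if the lower limit is above 0 m. The fixed order carries no alpha penalty.
3. State the matched pair of noninferiority and superiority powers: 80% and 55%, or 70% and 42%.
4. State that noninferiority without superiority will be reported as not worse by more than 12.5 m, and not as efficacy.

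Align the objective wording in Sections 1, 2 and 4. If substitution for center sessions is the reason for noninferiority, say so there.

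The cost is wording: no added patients or procedures. The price is candor about 42-55% superiority power and, if the 95% CI is chosen, a stated noninferiority power of about 70% instead of 80%. Powering superiority itself at 80% would mean randomizing 395 or 503 patients instead of 200.
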